6.2.2. Physical Examinations and Updated Physical Examinations

A full physical examination will be performed for those subjects that enroll in this study greater than one week following completion of the previous blinded study during the baseline visit by a qualified, licensed Doctor of Medicine (MD), Doctor of Osteopathy (DO), or physician assistant (PA). An updated physical examination will be performed for all subjects that enroll in this study at the Week 2 visit, Month 1 visit, Month 3 visit, Month 6 visit, Month 9 visit, Month 12 visit and every 6 month visit thereafter. At an End-of-Study visit, if a subject withdraws or is terminated from the study, a full physical examination will be performed.

A review of systems (ROS) will be included as part of the physical examination procedures. The ROS should include:

- Skin, hematological, cardiovascular, pulmonary, gastrointestinal, reproductive, neurological, psychiatric, lymphatic, endocrine, musculoskeletal, and/or drug allergies.
- Particular emphasis should be placed on careful elucidation of hematological, cardiac and cardiovascular, neurological and psychiatric conditions.

Findings will be documented in the subject's medical record and on the appropriate eCRF pages. Any significant changes from Day 1 (Baseline) are to be recorded during the updated physical examination and on the adverse event page for those subjects that enroll greater than one week following completion of previous study. Any significant changes from the last visit of the previous study are to be recorded during the updated physical examination and on the adverse event page for those subjects that enroll within one week following completion of previous study.

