6.2.7. Adverse Events

Adverse events will be recorded for all subjects during the Week 2 visit, Month 1 visit, Month 3 visit, Month 6 visit, Month 9 visit, Month 12 visit and every 6 month visit thereafter, and if a subject withdraws or is terminated from the study, at an End-of-Study visit.

Occurrence of AEs after the informed consent is signed and prior to the first administration of investigational drug in this study will be recorded as part of the Updated Medical History taken on Day 1 (Baseline). Once the first dose of investigational drug is taken on Day 1 any subsequent AEs are to be recorded on the CRF page for AEs.

All AEs must be followed until resolution, until the condition stabilizes, until the event is otherwise explained or is judged by the investigator to be no longer clinically significant, or until the subject is lost to follow-up. The investigator is responsible for ensuring that follow-up includes any supplemental investigations necessary to elucidate as completely as practical the nature and/or causality of the AE. This may include additionally laboratory tests or investigations histopathological examinations or consultation with other health care professionals.

Investigators are not obliged to actively seek AE information from former study participants. However, if the investigator learns of an SAE at any time after a subject has been discharged from the study and the event may reasonably be considered related to the use of the study drug, the investigator should promptly telephone the Medical Monitor.

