- **Highly Probable:** The event followed a reasonable temporal sequence from the time of investigational drug administration; and followed a known response pattern to the investigational drug; and could not be reasonably explained by other factors, such as the subject’s clinical state, therapeutic interventions, or concomitant medications administered to the subject; and either occurred immediately following investigational drug administration or improved on stopping the investigational drug or reappeared on repeat exposure.

Duration

The duration of the AE should be recorded using the following criteria:

- **Start:** Date of the first episode of the AE or date of significant sustained worsening in severity
- **Stop:** Date when AE either ceased permanently or changed in severity

Frequency

The duration of the AE should be recorded using the following criteria:

- **Single:** Experienced once, without recurrence
- **Recurrent:** More than one discrete episode with the same severity

Action Taken with Investigational Drug

- **None:** No change in study drug
- **Interrupted:** Investigational drug temporarily stopped
- **Discontinued:** Investigational drug discontinued permanently

Therapy

- **None:** No new treatment instituted
- **Medication:** New treatment initiated as a direct result of AE
- **Other:** Other action required

Outcome

- **Ongoing:** AE has not yet stopped
- **Resolved, no sequelae:** Subject has fully recovered
- **Resolved, with sequelae:** The AE has stopped, but the subject has a residual effect directly related to the AE
- **Death:** The subject died as a result of the AE
- **At Death, ongoing:** AE ongoing at time of subject death

Seriousness

- **Not serious:** Does not meet the criteria described in Section 6.2.7.2
- **Serious:** Meets the criteria described in Section 6.2.7.2

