Serious Adverse Event	
A serious adverse event (SAE) is any AE with any of the following outcomes:
 

• Results in death;

• Is life-threatening (i.e., the subject was at risk of death at the time of the event; it does not refer to an event which hypothetically might have caused death if it were more severe);

• Requires inpatient hospitalization or prolongation of existing hospitalization;

• Results in persistent or significant disability/incapacity;

• Is a congenital anomaly or birth defect;

• Is an important medical event that may not be immediately life-threatening or result in death or hospitalization but based on appropriate medical judgment may jeopardize the subject or may require medical or surgical intervention to prevent one of the outcomes listed above. Examples of such events are intensive treatment in an emergency room or at home for allergic bronchospasm; blood dyscrasias or convulsions that do not result in hospitalization; or development of drug dependency or drug abuse.

Scheduled Visit	
A scheduled visit is any planned visit per the protocol schedule of events.

Study Day 1	
Study day 1 is defined as the date of first administration of study drug (pimavanserin) in the ACP-103-015 study.

Study Day n	
Study day n represents a visit or assessment that occurs n days relative to the start of study drug in the ACP-103-015 study, computed as: (date of visit – study day 1) + 1 if the date of visit occurs on or after date of first dose; otherwise computed as: (date of visit – study day 1). Note that there is no day 0.

Study Duration	
The duration of the open-label use of pimavanserin will be determined based on clinical evaluations but may continue for as long as this drug is considered to be well tolerated and efficacious, and until such time as pimavanserin is approved and commercially available

Treatment- Emergent Adverse Event      A treatment-emergent adverse event (TEAE) is defined as an adverse event started between first study dose date and 30 days after the last dose date in the ACP-103-015 study.

Treatment Group      All subjects will receive 40 mg of pimavanserin once per day (QD).

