### 5.13.1 Adverse Events

AEs started between first study dose date and 30 days after the last dose date will be considered treatment-emergent AE (TEAEs). Any AEs with a completely missing start date will be considered as TEAEs. All AEs and TEAEs will be summarized. In addition, the number of TEAEs, and the number and percent of unique subjects with TEAEs will be summarized by system organ class (SOC) and preferred terms. For SAEs, the SAE onset date will be used in place of the AE onset date for the determination of treatment-emergent status and for assignment of the event to time windows and onset age groups.

AEs will be summarized in terms of the proportion of subjects as well as number of events. When calculating the proportion of subjects with AEs by time period or age group each subject will be counted in the numerator at most once and any repetitions will be ignored; the denominator will consist of all safety-evaluable subjects in the specified time period or age group. When calculating the number of events, each unique record in the database will be counted once.

Additional summaries of TEAEs will also be tabulated with respect to severity (mild, moderate, severe) and AEs of special interest. Tabulations will also be provided for AEs by maximum severity where a subject with more than one event coded to the same preferred term will be classified according to the most severe event. Similarly, in the tabulation by strongest relationship, a subject will be classified according to the event with the strongest relationship to study drug.

An overall summary of all AEs and TEAEs will be presented. The number and percent of unique subjects with TEAEs will be summarized by system organ class (SOC) and preferred term. The number and percent of unique subjects with TEAEs that are determined by investigators as related (possibly, probably, or definitely) to study drug will also be summarized by SOC and preferred term. Additional summaries of TEAEs will also be tabulated with respect to severity (mild, moderate, or severe), where a subject with more than one event coded to the same preferred term will be classified according to the more severe event. A summary of TEAEs in descending order of frequency by preferred term will also be tabulated. Listings of deaths, serious AEs and AEs leading to study treatment discontinuation will also be provided.

The tabulation of TEAEs will be grouped by (1) time period at AE onset and (2) age at AE onset.

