### **5.13.2 Deaths and Other Serious and Significant Adverse Events**

Treatment-emergent SAEs, TEAEs leading to discontinuation from the study or study drug, and TEAEs with fatal outcome will be summarized by time period as given in [Table 2](#) in frequency tables by SOC and preferred term. In addition, the overall AE summary table will also be presented for all events (i.e. treatment-emergent plus non-treatment-emergent events).

Subject listings of SAEs, deaths, and AEs leading to discontinuation of study drug will be provided. These listings will provide all relevant eCRF data for each event including the date/study day of onset, date/study day resolved, date of last dose/study day of last dose, severity, outcome, relationship to study drug, action taken, and seriousness.

Kaplan-Meier estimates of percent surviving subjects at 6 months, 1 year, 1.5 years, 2 years, 2.5 years, 3 years, 3.5 years and 4 years, as well as median survival time will be computed for all subjects and by subgroups: baseline age group ( $\leq 75$  years old or  $>75$  years old), gender (female or male), and geographic area (North America or outside North America). If a subject is deceased, the survival time will be calculated as death date minus first dose date + 1; otherwise the survival time will be censored at the last dose date (for subjects who have discontinued from the study) or database snapshot date (for ongoing subjects).

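### An AE carried over from core-study pimavanserin, non-serious and not significantly worse, is not a TEAE in -015, so the TEAE discontinuation tables omit it even if it makes the subject stop

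*Protocol*

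**What the plan says.** **Entry.** Protocol 3.1 allows entry at the last treatment visit of the blinded study, or up to 28 days after that treatment ends. SAP 5.11.1 names the prior treatments as placebo and pimavanserin 10, 20 or 40 mg. Some subjects can therefore pass from blinded to open-label pimavanserin without a break.

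**Recording.** Under Protocol 6.2.7, AEs after consent but "prior to the first administration of investigational drug in this study will be recorded as part of the Updated Medical History". AEs after that dose go on the AE page. Protocol 6.2.7.1 sets an AE's start as "Date of the first episode of the AE or date of significant sustained worsening in severity" and its stop as "Date when AE either ceased permanently or changed in severity".

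**Treatment-emergent status.** The SAP Definitions require an "adverse event started between first study dose date and 30 days after the last dose date in the ACP-103-015 study", and SAP 5.13.1 repeats the rule. For SAEs, 5.13.1 substitutes the SAE onset date. A wholly missing start date counts as treatment-emergent, and SAP 5.4.3 moves some partial dates to Day 1.

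**Tables limited to TEAEs.** SAP 5.13.1 tabulates TEAEs leading to discontinuation by period and by age at onset. SAP 5.13.2 tabulates "TEAEs leading to discontinuation from the study or study drug" by system organ class and preferred term within period. In SAP Table 2 the AE-onset column has no baseline cell and starts at Day 1.

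**Outputs not limited to TEAEs.** These are disposition by withdrawal reason (SAP 5.5), the Kaplan-Meier analysis of AEs leading to termination or withdrawal (5.7.1), the listings of AEs leading to discontinuation (5.13.1, 5.13.2) and one overall AE summary of all events (5.13.2).

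**The concern.** Tolerability is part of the primary objective, and AEs are the first measure named for it in Protocol 6.1. For a subject who arrives from a pimavanserin arm, exposure may be unbroken while the AE clock restarts at the first -015 dose. An AE that began on the drug and simply persists then counts as pre-existing. If the subject eventually gives up because of it, the exit is a tolerability failure on pimavanserin, yet the tables that say which AEs led to stopping have no place for it. A former-placebo subject who develops the same AE on first exposure in -015 is counted.

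The SAP recognises this issue for one safety measure. In 5.13.5.1 it adds a pre-pimavanserin ECG baseline, taken from before the core study's exposure. AEs have no counterpart, and the AE tables are not split by prior treatment, so a reader could not see the asymmetry.

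There is also a recording gap. Protocol 6.2.7 covers AEs between consent and first dose, and AEs after first dose. It does not say where an AE already ongoing from the core study is held.

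**Working it through.** The plan states no figure that depends on this point, so the check applies the written rules to types of event. The dates are assumed for illustration: first -015 dose 15 March 2010, last dose 15 March 2011.

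**Rule.** An AE is a TEAE if first dose ≤ start date ≤ last dose + 30 days. With these dates the window runs from 15 March 2010 to 14 April 2011. Start dates follow Protocol 6.2.7.1, SAP 5.4.3 and the SAE rule in SAP 5.13.1.

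| Event | Start date used | TEAE? |
|---|---|---|
| Core onset 20 Feb 2010, same severity, non-serious | 20 Feb 2010 | No |
| Core onset, day missing, month before first dose | 1 Feb 2010 | No |
| Onset 14 Mar 2010, after consent and before first dose | 14 Mar 2010 | No |
| Core onset, significant sustained worsening on Day 60 | 13 May 2010 | Yes |
| Core onset, becomes serious on Day 90 | 12 Jun 2010 | Yes |
| Core onset, day missing, same month as first dose | 15 Mar 2010 | Yes |
| Core onset, month and day missing, same year as first dose | 15 Mar 2010 | Yes |
| Start date wholly missing | 15 Mar 2010 | Yes |

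The first row is the carried-over AE at issue; the second is the same case with an incomplete date.

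**Following the first row to an exit.** Suppose this subject stops the drug because of that AE.

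1. *TEAE discontinuation tables (5.13.1, 5.13.2):* not counted. The AE is not a TEAE, and Table 2 has no AE period before Day 1.
2. *Disposition (5.5):* counted if the investigator gives adverse event as the withdrawal reason. This does not depend on an AE record.
3. *Kaplan-Meier (5.7.1):* counted, at last dose date minus first dose date + 1, provided the AE is recorded in -015 as leading to withdrawal.
4. *Listings and all-event overall table:* can show it, on the same proviso.

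Protocol 4.2 requires an AE that ends participation to be reported under 6.2.7, which supports the proviso. But 6.2.7 has no rule for an AE with onset in the core study. If it were held only in medical history, items 3 and 4 could miss it too.

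**Scale.** The documents give neither the number of AEs ongoing at rollover nor the number of subjects from pimavanserin arms. Protocol 3.4 anticipates at least 400 subjects, so one omitted subject is at most 1/400 = 0.25 percentage points of that total. Within a period the denominator is the number of subjects on treatment then, so one subject weighs more once that number falls below 400.

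**The case against.** The strongest defence is that counting AEs from the first dose of the study is a clear, prespecified rule, and that the other outputs remain available. Much of this stands, and it rules out several stronger readings.

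- *Carried-over AEs can never be treatment-emergent.* The table shows otherwise. Significant sustained worsening gives a new start date, SAEs use their own onset date, and some incomplete dates become Day 1. An AE tolerated at rollover that later forces a stop may well have worsened or become serious, so these rules narrow the discontinuation case in particular.
- *These exits vanish from the report.* They do not. Disposition, Kaplan-Meier, the listings and the all-event table have no TEAE restriction. A difference between them and the TEAE tables is a difference of stated scope and not a contradiction, although no reconciliation is planned.
- *Protocol 6.2.7 sends core-study AEs to medical history.* Its sentence begins "Occurrence of AEs after the informed consent is signed and prior to the first administration of investigational drug in this study", so it covers only the gap between consent and first dose. Likewise, "Any significant changes from the last visit of the previous study are to be recorded" in Protocol 6.2.2 governs physical examination findings in early entrants, not AEs in general.
- *Treatment is continuous for everyone.* Entry may come up to 28 days later, and some subjects come from placebo or another dose. Inclusion criterion 1 also requires that the investigator think the subject may benefit, which makes rollover with a poorly tolerated AE less likely.

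What the defence does not answer is that the planned discontinuation tables by preferred term omit a known kind of on-drug tolerability failure. The all-event table is described only as an overall summary.

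**Conclusion.** The point holds for a defined class: AEs that began on core pimavanserin, have a known onset before the first -015 dose, stay non-serious and do not significantly worsen. They are outside the TEAE tables, including those for discontinuation, whatever their consequence. This follows from the SAP's wording and needs no assumption. It is a gap in the tolerability tables that is cheap to close, and it leaves new-onset counts untouched.

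Its size is unknown. A reader might try assumed inputs: 200 to 270 subjects from pimavanserin arms, of whom 1% to 5% stop for such an AE. That gives 200 × 0.01 = 2 to 270 × 0.05 = 13.5 subjects, or 0.5 to 3.4 percentage points of 400. The documents support neither input, and the percentages make no allowance for the worsening, seriousness and date rules. Nor would the result be a loss from the overall AE-discontinuation rate, which disposition and Kaplan-Meier can still show. Only the TEAE tables would be affected.

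**What to change.** In SAP 5.13.1 and 5.13.2:

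1. Tabulate all AEs leading to discontinuation by system organ class and preferred term, regardless of onset date. Assign those with onset before Day 1 to a period and age group by discontinuation date. The SAP already places fatal TEAEs by time and age at death, so the principle is not new to it.
2. Show AEs with onset on core pimavanserin that were ongoing at the first -015 dose in a separate column, not added to the new-onset counts.
3. Write the worsening rule of Protocol 6.2.7.1 into the TEAE definition, so that it no longer depends on how sites split records.
4. State where an AE ongoing from the core study is recorded in -015, and footnote why disposition, Kaplan-Meier and the TEAE tables may differ.

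The cost is SAP wording and a merge with core AE data. The SAP already draws on the core studies for baseline measurements, but not for AE records, so the merge is additional work and needs stated conventions. The tabulated AE-discontinuation count may become slightly less favourable.

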- (1) AEs grouped by time period at AE onset: For all TEAEs, serious TEAEs, TEAEs leading to discontinuation of study drug, and TEAEs of special interest (those that may be expected on the basis of pimavanserin's pharmacology, those of special regulatory interest [suicidality, abuse liability etc], and those commonly associated with current antipsychotics), the count and percentage of subjects will be summarized by time period defined in [Section 5.4.2 Table 2](#). The denominator for a time period will be the number of subjects on treatment

(including a 30-day follow-up) during that particular time period. TEAEs with fatal outcome will be summarized by time period at death.

- (2) AEs by age group at AE onset: For all TEAEs, serious TEAEs, TEAEs leading to discontinuation of treatment, and TEAEs of special interest, the count and percentage of subjects will be summarized by age category at the time of AE onset. Age at onset will be categorized as follows:  $\leq 50$  years, 51 - 60 years, 61 – 70 years, 71 – 80 years and 81 - 90 years. The denominator for an age group will be the number of subjects on treatment (including a 30-day follow-up) while in that particular age group. TEAEs with fatal outcome will be summarized by age group at death.

An AE listing by subject will display all events and will include the verbatim term in addition to the MedDRA SOC and preferred term. This listing will also include all relevant CRF data associated with the event: date of onset, date of last dose, severity, outcome, relationship to study drug, action taken, and seriousness.

In addition, AE tables also will be summarized by age group and onset time period for subject with concomitant antipsychotic use and without antipsychotic use.

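### The SAP counts adverse events and subjects at risk to 30 days after last dose, but the protocol schedules no adverse-event collection after an End-of-Study visit of undefined timing

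*Protocol*

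**What the plan says.** **SAP.** The Definitions section counts as treatment-emergent any "adverse event started between first study dose date and 30 days after the last dose date in the ACP-103-015 study". Section 5.13.1 repeats this. Neither place sets a causality condition. For the tables by age at onset, the denominator is the "number of subjects on treatment (including a 30-day follow-up) while in that particular age group"; the time-period denominator is built the same way. Section 2.2, however, describes adverse-event monitoring as running from consent only to the last visit.

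**Protocol.** Section 6.2.7 has adverse events recorded at each scheduled visit "and if a subject withdraws or is terminated from the study, at an End-of-Study visit". Sections 3.1 and 3.6.2.5 and Table 1 give that visit no day count or window relative to last dose, and nothing is scheduled after it. For people who have left, 6.2.7 states that "Investigators are not obliged to actively seek AE information from former study participants". It adds that the Medical Monitor should be telephoned if the investigator learns of a serious event after discharge and "the event may reasonably be considered related to the use of the study drug". Section 4.2 stops data collection for subjects who withdraw consent, except for events already ongoing.

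**The concern.** The analysis window is longer than the window in which events are looked for. Between the End-of-Study visit and day 30, subjects count as at risk although nobody has to ask them about new events. What does arrive has passed a relatedness judgement that the treatment-emergent definition does not use.

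Long-term safety and tolerability is the only objective (Protocol 2). The Protocol background raises mortality with antipsychotics in elderly patients. The SAP (5.12) describes an interim analysis for a marketing application and no data safety monitoring board. A serious event or death shortly after stopping, from a new cause the investigator does not think related, is the kind most likely to be missed. The survival analysis (SAP 5.13.2) treats post-dose time differently again: it censors discontinued subjects at last dose but counts deaths at the date of death with no stated limit.

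**Working it through.** The plan has no figure to reproduce: SAP 2.4 marks sample size as not applicable, and neither document assumes a discontinuation rate. The check is a comparison of the texts, followed by an illustration of size.

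**Step 1: the window, piece by piece.**

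- *Last dose to End-of-Study visit.* The SAP counts events and subjects. The protocol records events of any kind and any causality. The length of this interval is not given.
- *End-of-Study visit to day 30.* The SAP still counts both. The protocol has no visit or call. Known events are followed up (4.2, 6.2.7, and the serious-event text of 6.2.7.2), but the rule for new onsets after discharge is passive and limited to possibly related serious events.
- *After consent withdrawal.* The SAP makes no exception. The protocol collects no new events.

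**Step 2: how much of the window is actively covered.** If the End-of-Study visit falls d days after last dose, the covered share is d/30.

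- d = 0: 0/30 = 0%
- d = 3: 3/30 = 10%
- d = 7: 7/30 = 23%
- d = 14: 14/30 = 47%
- d = 30: 30/30 = 100%

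The documents fix none of these. Some text suggests a short interval. Protocol 3.1 requires a separate visit only when a subject stops between planned visits. Protocol 8 places that visit's drug-level sample before dosing on the day. SAP 5.4.1 accepts rating-scale data only to last dose + 3 days. That is inference, not a stated rule.

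**Step 3: effect on period percentages.** Inputs: the 30 days (SAP Definitions and 5.13.1); 400 subjects (Protocol 3.4, an anticipated minimum, used only for scale); and 12-month retention R, which is **assumed** at 85% to 40%. With a constant stopping hazard:

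- λ = −ln(R)/365 per day.
- For a period starting at least 30 days after first dose, the denominator grows by the factor exp(30λ).
- If the added subjects contribute no recorded events, a true 10% reads as 10% × exp(−30λ).
- Added subjects at day 92 (start of the >3–6 month period): 400 × [exp(−61λ) − exp(−91λ)].
- Off-drug share of at-risk time: 30λ/(1 + 30λ).

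For R = 70%: λ = 0.3567/365 = 0.00098 and 30λ = 0.0293. The factor is 1.030, and 10% × 0.971 = 9.7%. The added subjects are 400 × (0.9421 − 0.9149) = 10.9.

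| Assumed R | λ per day | Denominator growth | Relative dilution | Added of 400 | True 10% reads | Off-drug time |
|---|---|---|---|---|---|---|
| 85% | 0.00045 | 1.3% | 1.3% | 5 | 9.9% | 1.32% |
| 70% | 0.00098 | 3.0% | 2.9% | 11 | 9.7% | 2.85% |
| 55% | 0.00164 | 5.0% | 4.8% | 17 | 9.5% | 4.68% |
| 40% | 0.00251 | 7.8% | 7.3% | 25 | 9.3% | 7.00% |

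These are upper bounds, because they give the added subjects no recorded events at all. Such a subject also spends at most 30 days in the next period, while the >6–12 month period lasts 365 − 184 + 1 = 182 days. Part of the dilution would therefore remain even with complete collection.

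**Step 4: what the arithmetic does not size.** The documents give no rate of serious events or deaths after stopping, so the number that could be missed cannot be computed.

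**The case against.** A reader might infer that almost nothing is collected in the 30 days except serious events judged related, and hence that deaths and serious events are under-counted. The documents do not support that.

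- The rule in 6.2.7 concerns people already discharged, not everyone off drug. All events up to and at the End-of-Study visit are recorded, and that visit could fall anywhere in the window.
- Known events are followed until they settle. Extra visits are allowed when medically indicated (4.2), and serious events are to be reported within 24 hours of discovery with no causality filter in that text. An on-treatment event that later proves fatal should therefore be captured.
- A known death enters the survival analysis with no relatedness test.
- The available text of 6.2.7.2 breaks off within the seriousness criteria and resumes mid-sentence. A reporting period for serious events may have stood there, and its absence cannot be held against the plan.
- SAP 5.14.4 lists telephone contacts to assess tolerability, though without timing and with no matching entry in the protocol schedule.
- The retention figures are assumed, the dilution is small, and no formal tests are planned.

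All of this stands and limits the point. It does not close the gap: following known events does not find new ones, and the specific rule for discharged subjects is passive and filtered by relatedness. A reporting period in the missing text would have to be reconciled with 6.2.7, and it need not cover the non-serious events that the SAP also counts.

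**Conclusion.** The point holds as a mismatch between the analysis window and the stated collection window. It is established for new events after the End-of-Study visit and after consent withdrawal, on the visible text, and subject to whatever 6.2.7.2 says in full.

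The distortion of pooled period percentages is minor: a relative dilution of about 1% to 7% at most, resting on a constant stopping hazard, assumed 12-month retention of 85% to 40%, and no recorded events among the added subjects. The first 4 weeks are unaffected.

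The more important consequence is qualitative. In a study whose sole objective is safety, counts of serious events and deaths soon after stopping would be incomplete and partly filtered by causality, yet reported under a definition that ignores causality. How many are lost, if any, cannot be said from the documents. The windows should be aligned. The mismatch is not a reason to discard the on-treatment summaries.

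**What to change.** 1. **Protocol 6.2.7, reconciled with 6.2.7.2:** require that any serious event or death the site learns of, with onset within 30 days of last dose, be recorded regardless of relationship to study drug.
2. **SAP 5.13.1:** use one common cutoff for both numerator and denominator of the time-period and age-group tables, namely the later of last dose and the last adverse-event assessment, capped at last dose + 30 days. This also handles subjects who withdraw consent. Shortening only the denominator would not do, because a subject could then appear in a period's numerator but not its denominator.
3. **Reporting:** keep the 30-day version as a sensitivity table, and show serious events and deaths after the cutoff separately.

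**Cost.** The SAP change is wording plus one extra set of tables and needs no new data. The protocol change is short wording, but it is an amendment needing ethics approval and investigator agreement (Protocol 13.5) across approximately 150 sites. It cannot recover events in subjects who have already left, including those who left before the 13 December 2013 snapshot. No additional visit or telephone call is needed to align the windows.
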